#### **5.1 Study Design**

This is a prospective, multi-center, intention-to-treat safety and feasibility study. Subjects will undergo percutaneous PEF ablation for pulmonary vein isolation. Subjects will then be followed at 7 days, 30 days, 75 days, 90 days, 6 months, and 12 months for adverse events, recurrence of arrhythmia after a 90-day blanking period and other relevant outcome measures.

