#### **5.8 Enrollment**

Subjects that meet all of the eligibility criteria and are deemed suitable by the investigator will be invited to participate in the study.

Subjects will be considered enrolled at the time of signing the Informed Consent Form.

Each subject will be assigned a unique study identification code to protect each subject's confidential health information. The unique study identification code will not include date of birth or subject's first and last initials and will be used to link study data and other study information to the subject in lieu of the subject name. The Subject Name Log will be used to link the unique study identity code to the subject and will be maintained at the site. This log will remain confidential and will not be provided to the Sponsor, but only used for reference when monitoring at the study site.

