## 7. Statistical Analysis and Endpoint Assessment

### 7.1 General Statistical Considerations

The primary objective of this study is to further characterize the safety and feasibility of the FARAPULSE Endocardial Ablation System in subjects with paroxysmal atrial fibrillation.

This is a feasibility study with no formal hypothesis testing and therefore no required sample size. Study results will be presented using descriptive statistics. Results from this study will be used to inform and design additional clinical studies.

All subjects will be followed on an Intent-to-Treat basis. The device performance will be assessed based on an intent-to-treat analysis of the primary safety and feasibility endpoints, and secondary feasibility endpoints. A per protocol analysis, along with other secondary analyses, will also be reported.

An intent-to-treat analysis of device performance will be assessed as the number of patients in whom all pulmonary veins are electrically isolated using only the study device at the completion of the index procedure.

All subjects who meet enrollment criteria for the study and undergo catheterization and ablation procedures with the FARAPULSE Endocardial Ablation System shall be included in the Intent-to-Treat cohort/population. This will exclude any patients in whom exclusion criteria were identified prior to any ablation with the study device.

Demographic, baseline clinical and disease characteristics, procedural results and primary, secondary and all additional endpoints will be summarized using descriptive statistics.

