### **9. Monitoring**

#### **9.1 Study Monitoring**

Clinical monitors, qualified by training and experience, will be responsible for monitoring and overseeing the conduct of the study. The clinical monitors will evaluate compliance with the protocol, any specific recommendations made by the site's Ethics Committee (EC) and the signed Investigator Agreement. Phone contacts and site visits will be conducted to ensure that the protocol is being followed and that any protocol deviations are properly documented. Clinical monitoring will include a verification that Informed Consent Form was properly obtained for all enrolled study participants, a review of clinical records for accuracy and completeness, resolution of missing or inconsistent results and a review of source documents. The clinical monitor will verify that the Case Report Forms (CRFs) are in agreement with the source documentation and other records. The Investigator will make available to the clinical monitor for review all Informed Consent Forms, all completed CRFs, source documentation and other relevant records for all enrolled subjects at the site.

If a deficiency is noted during an on-site monitoring visit or at any other time during the course of the study, the clinical monitor is required to discuss the situation with the Investigator and the Sponsor to ensure compliance.

The Sponsor or its designated representative, qualified by training and experience, will be responsible for monitoring and overseeing the conduct of the study. The accuracy of all collected data will be verified for:

- Eligibility criteria
- Baseline characteristics
- Primary safety and feasibility endpoints
- Secondary endpoints
- Adverse events (including SAEs) and Device Deficiencies / Malfunction Reporting

with source documents including, but not limited to, medical records, office/ clinic notes, procedure reports, laboratory results, physician and nursing progress notes.

Verification and quality of data, monitoring of clinical study progress and Investigator compliance with the approved protocol will be conducted by the Sponsor or its designated representative.

It is important that the Investigator and other relevant site personnel, including the research study coordinator, are available for consultation with the clinical monitors during the monitoring visits and that sufficient time is devoted at the site for the monitoring process.

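### The two sentences in Section 7.1 that define the ITT set do not agree on ablated subjects with an eligibility breach, and on the wording some of them fall outside the primary safety and feasibility analyses.

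*Combined protocol and SAP*

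**What the plan says.** Section 5.1 labels the design: "This is a prospective, multi-center, intention-to-treat safety and feasibility study". Section 7.1 then assigns endpoints to the analysis: "The device performance will be assessed based on an intent-to-treat analysis of the primary safety and feasibility endpoints, and secondary feasibility endpoints".

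Section 7.1 defines the set in two sentences. The first admits "All subjects who meet enrollment criteria for the study and undergo catheterization and ablation procedures with the FARAPULSE Endocardial Ablation System". The second adds: "This will exclude any patients in whom exclusion criteria were identified prior to any ablation with the study device".

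Section 7.1 also promises a second analysis, "A per protocol analysis, along with other secondary analyses, will also be reported", but does not define its set. Section 7 contains no safety or as-treated set.

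Two other sections bear on the point. Under Section 5.8, "Subjects will be considered enrolled at the time of signing the Informed Consent Form", so enrolment precedes ablation. Section 9.1 says "The accuracy of all collected data will be verified for" a list of items against source documents. Eligibility criteria head that list, and nothing requires the check to be finished before the procedure.

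**The concern.** In a single-arm study of an investigational ablation system, everyone who received the study energy should count in the primary safety result. The first sentence of the definition makes eligibility a condition of membership. Eligibility can be re-examined at source verification, after the procedure and possibly after an outcome is known. Some criteria also involve judgement, such as living locally (Section 5.2.1) or having a clinically significant arrhythmia other than AF (Section 5.2.2).

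At stake is the chance that a device-exposed subject leaves the primary denominator for a reason that could be settled with the outcome in view. With at most 80 subjects, one event changes the reported rate visibly. Section 7.2 says that these estimates will inform the powering of a later pilot study.

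**Working it through.** The plan states no power, margin, expected event rate or expected number of ineligible subjects, so there is no figure of its own to reproduce. The check is a reading of the two sentences case by case, followed by an illustration of size.

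**Step 1. Apply both sentences of the definition to subjects ablated with the study device.**

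| Ablated subject | First sentence (eligible and ablated) | Second sentence (exclusion found before ablation) | Result on the wording |
|---|---|---|---|
| Meets all criteria | Admitted | Does not apply | In |
| Failed an inclusion criterion | Not admitted | Silent: names exclusion criteria only | Out |
| Exclusion criterion found only after ablation | Not admitted if read alone | Implies that the subject is kept | Not aligned; staying in is the better reading |
| Exclusion criterion identified beforehand, ablated anyway | Not admitted | Removed | Out under both |

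The second row covers the items in Section 5.2.1: AF documentation, episode count, drug failure, age and the participation requirements. The fourth row arises only through a protocol deviation, but the second sentence is not confined to subjects who never went on to ablation, so it reaches them.

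**Step 2. Look for another set that would catch the omitted subjects.** Section 7.1 names only the ITT and per-protocol analyses. The statement "All subjects will be followed on an Intent-to-Treat basis" concerns follow-up and does not set the denominator.

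**Step 3. Illustrate the size.** From the documents: n = 80, the maximum planned enrolment (Section 5.4). Assumed: all 80 are ablated, x = 3 have a composite event, k = 4 ablated subjects (4/80 = 5%) are left out, and j of those four had an event.

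Rate before = x/n. Rate after = (x − j)/(n − k). Exact (Clopper-Pearson) 95% limits for x events in n are the 2.5% point of Beta(x, n − x + 1) and the 97.5% point of Beta(x + 1, n − x).

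- All kept: 3/80 = 3.75% (0.78 to 10.57).
- j = 1: (3 − 1)/(80 − 4) = 2/76 = 2.63% (0.32 to 9.18).
- j = 0: 3/(80 − 4) = 3/76 = 3.95% (0.82 to 11.11).

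The rate falls when j/k exceeds x/n, that is, when j is above 4 × 3/80 = 0.15. In this example any event among the four lowers the rate, and no event among them raises it slightly.

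The primary feasibility endpoint (acute procedural success) moves in the same way. Assume 78 successes in 80: 97.5% (91.3 to 99.7). If the two failures were the subjects left out, 78/78 = 100% (95.4 to 100).

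**The case against.** The strongest reply is that the second sentence explains what the first leaves out. If every ineligible subject were already removed whenever found, limiting the exclusion to the time before ablation would do no work. Section 5.8 also suggests that eligibility is a status at entry: subjects judged to meet the criteria are invited and count as enrolled once they consent. Section 9.1 has monitors verify eligibility, but gives no rule for moving anyone between analysis sets.

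Much of this stands. A reader might infer from the first sentence alone that any subject ablated and later found ineligible drops out of the primary results. The documents do not support that for exclusion criteria found only after ablation. These include the breaches one would most readily associate with risk: low ejection fraction, recent pericardial effusion and other significant arrhythmias are all exclusion criteria in Section 5.2.2.

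Nor would an omitted subject's event vanish from the study. Section 8.2 requires all adverse events to be recorded. Section 10.10 has the events committee adjudicate procedure-related and serious events and the safety board review safety data. Section 7.1 does not name the secondary safety endpoints among those analysed by ITT. Section 10.5 requires deviations to be reported in the final clinical report. What would change is the primary numerator and denominator.

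The reply does not dispose of the second and fourth rows of the table. The second sentence does not mention inclusion criteria, and it expressly removes a subject whose exclusion criterion was known before ablation, even if ablation followed.

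**Conclusion.** The point holds as a defect of wording with a limited reach. The set used for the primary safety and feasibility endpoints omits two kinds of device-exposed subject: those who failed an inclusion criterion, and those ablated despite an exclusion criterion already identified. For exclusion criteria found only after ablation, the text implies retention but does not say so.

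The size cannot be derived from the documents. With the assumed 4 breaches and 3 events among 80, the composite rate moves from 3.8% to 2.6% or to 3.9%, depending on whether one or none of the four had an event. The intervals overlap almost entirely, and the study is descriptive with no hypothesis test. If no ablated subject of either kind occurs, and later-found exclusions are kept as implied, the effect is zero.

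A reader might also infer that the plan sets out to remove subjects after seeing their outcome. No sentence says that. The wording merely leaves room for it. The point concerns ablated subjects only; procedures that end before ablation are a separate question.

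**What to change.** In Section 7.1:

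- Delete the eligibility condition from the first sentence of the ITT definition, so that ablation with the study system decides membership.
- Limit the second sentence to subjects who were never ablated with the study device.
- State that every subject who received study-device ablation stays in the primary safety and feasibility analyses, whatever the eligibility finding and whenever it is made.
- List eligibility violations in the report, and exclude those subjects only from the per-protocol analysis, whose set should be defined to say so.

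The cost is a wording change, with no added visits, data or subjects. The one downside for the sponsor is that the safety figure may come out slightly less favourable.

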### 7.2 Sample Size Justification

The subject investigation is an expansion of the PEFCAT safety and feasibility study. A total of up to 80 patients will be studied at two centers to allow for continued assessment of the FARAPULSE Endocardial Ablation System and gain additional investigator experience. The subject investigation will be used to inform

the clinical dosage and procedural requirements to support a subsequent Pilot Study.

The safety and feasibility of the device will be analyzed before embarking on larger fully powered clinical studies to analyze safety and effectiveness of the FARAPULSE Endocardial Ablation System.

The sample size of up to 80 patients at two sites will allow event rate estimates for safety and device performance and associated confidence intervals. Two participating centers allow the collection of safety and feasibility data from multiple clinical users. These data will be used to inform the statistical powering of a future pilot study.

### **7.3 Demographic, Safety, Feasibility and Effectiveness Data**

Demographic and baseline clinical and disease characteristics will be summarized in tables. For continuous variables, the summary will include number, mean, and standard deviation and 95% bilateral confidence intervals, where pertinent.

Summaries for categorical variables will include the number and percent of subjects in each category.

### **7.4 Imputation for Missing Data**

Imputations for missing data in (e.g., withdrawn subjects, loss to follow-up, missing data) will not be performed. Analyses will be performed with all available data only.

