#### **5.12.5 75 Day Follow-Up**

Subjects will return for an office visit at 75 days ( $\pm$  15 days) post index ablation. At a minimum, the following data will be collected at the 75-day follow-up visit:

- Medications including use, changes in or discontinuation of anticoagulation, rate control and/or antiarrhythmic medications
- Pregnancy test (if applicable)
- Cardiac rhythm as determined by a 12-lead ECG
- Cardiac CT or MRI scan to assess the patency of the pulmonary veins
- 3D electroanatomical remapping procedure to assess electrical isolation of the pulmonary veins. Any electrical gaps may be closed at the investigator's discretion using a commercially approved ablation device. This will consist of placement of catheters in the left atrium via femoral access and transseptal puncture using conventional electrophysiology techniques. Any electrical gaps may be closed at the investigator's discretion using the study device or, if clinically necessary, using a commercially approved ablation device (which constitutes a therapeutic treatment failure).

- An Event Monitor will be provided to be used up to the 12-month follow-up visit for weekly scheduled and ad hoc symptomatic monitoring. Subjects will retain this device through the 12-month follow-up, ECG data from this monitor will be analyzed by a contract core lab. Investigational sites will be provided with the Event Monitor device and instructions for its use by the contract core lab. The investigational sites will then provide the device and instructions for use to the subject. The Event Monitor will be returned at the end of the subject's follow-up using shipping materials provided by the core lab.
- Cardioversions since last visit
- Heart failure status as assessed by NYHA classification at the time of visit
- Fluoroscopic Examination of Diaphragm Motion if the procedural examination indicates diminished phrenic nerve response
- Anticoagulation Monitoring: For subjects on anticoagulants, assessment of INR/PTT therapeutic levels as applicable/required (maintain as clinically indicated)
- Any additional ablation procedures performed
- Any hospital readmissions, including admission and discharge dates, since the previous visit
- Adverse Events

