### 5.14 Study Exit or Premature Withdrawal

Once the subject has completed the final follow-up visit they can be exited from the study provided that they do not have any conditions that require continued follow-up.

If a patient withdraws from the study prematurely or is withdrawn based on the judgement of investigator, the site will document the reason for withdrawal and inform the Sponsor. These patients will continue to be followed for safety through the 12-month timepoint.

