#### **7.5.2 Secondary Feasibility Endpoint**

1. The proportion of subjects that achieve Chronic Procedural Success (CPS) defined as persistent electrical isolation of all initially ablated pulmonary veins assessed during an electroanatomical mapping procedure performed 75 days following the index procedure. Chronic Procedural Success will be subdivided by single procedure and reablated subjects.
2. The proportion of subjects that achieve Therapeutic Success, defined as freedom from:
  - a. Post blanking period through assessment: occurrence of AF, AFL or AT, or ablation for AF/AFL/AT using the study device
  - b. At any time: ablation for AF/AFL/AT with a nonstudy device

Therapeutic success will be assessed from the end of the blanking period at Months 6 and 12, and will be subdivided by on / off AFDs post blanking period.

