### 7.6.2 Secondary Safety Endpoint

1. The proportion of subjects reporting one or more device- or procedure-related SAEs, as assessed at 30 days, 75 days, 6 months and 12 months of follow-up.
2. The proportion of subjects with stroke or TIA through 12 months
3. The proportion of subjects with major bleeding related to anticoagulation treatment through 12 months
4. The proportion of subjects requiring cardioversion through 12 months

5. The proportion of subjects requiring an arrhythmia-related hospitalization through 12 months

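### Therapeutic Success is event freedom over time, but the plan reports a simple proportion and gives no rule for ITT subjects who leave while still event-free

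*Combined protocol and SAP*

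**What the plan says.** Section 7.5.2 (repeating 5.3.4) introduces the endpoint as "The proportion of subjects that achieve Therapeutic Success, defined as freedom from" two kinds of event. The first is AF, AFL or AT, or study-device ablation, between the end of blanking and the assessment. The second is "At any time: ablation for AF/AFL/AT with a nonstudy device". The endpoint is read at Months 6 and 12, and the blanking period is 90 days.

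On the population, Section 7.1 states: "The device performance will be assessed based on an intent-to-treat analysis of the primary safety and feasibility endpoints, and secondary feasibility endpoints". It defines that cohort: "All subjects who meet enrollment criteria for the study and undergo catheterization and ablation procedures with the FARAPULSE Endocardial Ablation System shall be included".

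On method, Section 7.1 plans descriptive statistics with no hypothesis test, and Section 7.3 summarises categorical variables by number and percent. Section 7.4 excludes imputation for withdrawn or lost subjects and adds "Analyses will be performed with all available data only". No censoring rule, life table or Kaplan-Meier estimate is mentioned anywhere.

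Withdrawal and loss to follow-up are foreseen in Sections 5.9, 5.10 and 5.14. On withdrawn subjects, 5.14 says "These patients will continue to be followed for safety through the 12-month timepoint". On rhythm data, Section 5.12.5 says: "An Event Monitor will be provided to be used up to the 12-month follow-up visit for weekly scheduled and ad hoc symptomatic monitoring".

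**The concern.** A subject with a recurrence at month 4 is an observed failure whatever happens later. A subject who is event-free to month 8 and then lost has no 12-month result, only 8 months of partial information. A simple proportion cannot use that information. Dropping the subject departs from Section 7.1; assigning success or failure is in effect the imputation that Section 7.4 excludes. The two sections cannot both be followed for such a subject, and nothing says which gives way.

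This is the study's only freedom-from-arrhythmia endpoint. Section 7.2 says the data will inform the powering of a future pilot study, though it does not name this endpoint. In a descriptive study the estimate is the product, so its denominator should be fixed before the results are known.

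**Working it through.** The documents give no Therapeutic Success rate and no dropout rate, so there is no figure of the plan's own to reproduce. The check asks how far the possible conventions differ.

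**Inputs.**
- N = 80 (Section 5.4), blanking to day 90, landmark at day 365, leaving 275 days at risk.
- True 12-month freedom S = 70%, assumed. The 20–40% recurrence figure in Section 3.5 suggests 60–80% as an illustrative range.
- Random dropout D = 5, 10 or 20% per year from the index procedure, assumed.
- Constant hazards.

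**Formulas.**
- Event hazard after day 90: h = −ln(S)/275. For S = 0.70, h = 0.001297 per day.
- Dropout hazard: d = −ln(1−D)/365.
- Observed failures: F = exp(−90d) × h/(h+d) × [1 − exp(−275(h+d))].
- Event-free completers: C = S(1−D).
- Event-free leavers: 1 − C − F.

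**Example, D = 10%.** d = 0.000289. F = 0.9744 × 0.8180 × 0.3534 = 0.2817. C = 0.70 × 0.90 = 0.630. Leavers = 0.088, about 7 of 80. Keeping observed failures and dropping event-free leavers gives C/(C+F) = 0.630/0.9117 = 0.691.

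**Results for S = 70%.**

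| Dropout per year | F | C | Event-free leavers | C/(C+F) | Difference from 70% |
|---|---|---|---|---|---|
| 5% | 0.2909 | 0.665 | 0.044 | 69.6% | −0.4 |
| 10% | 0.2817 | 0.630 | 0.088 | 69.1% | −0.9 |
| 20% | 0.2627 | 0.560 | 0.177 | 68.1% | −1.9 |

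At S = 60% the differences are −0.5, −1.0 and −2.2 points; at S = 80% they are −0.3, −0.7 and −1.5. If the same dropout fraction falls wholly after blanking, S = 70% gives 69.4, 68.8 and 67.4%. The largest shortfall over the whole range is then 3.0 points (S = 60%, D = 20%).

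**Completers only.** Under random dropout this is unbiased, because leaving is unrelated to outcome. It discards failures already observed in subjects who later left. Its standard deviation is √(0.70 × 0.30/72) = 0.054 at 10% dropout and √(0.21/64) = 0.057 at 20%.

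**Kaplan-Meier.** In a 10,000-run simulation with N = 80 and dropout after blanking, the mean was 70.0% at both 10% and 20% dropout, with standard deviations of 0.053 and 0.055. It is unbiased and slightly more precise than completers only.

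**Scale.** The exact 95% CI for 56/80 is 58.7–79.7%, about 21 points wide.

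**The case against.** The strongest reply is that the plan does not commit to a biased estimator. Section 7.4 says only no imputation and all available data. Kaplan-Meier imputes nothing, uses every available day and is descriptive, so it already fits. The wording of 7.5.2 can also be read as a proportion of those assessed at each landmark, which is unbiased under random dropout. Inclusion criterion 3 asks for local residence and willingness to attend all visits, and Section 10.2.4 reimburses travel, so losses may be low. With complete follow-up all the methods coincide.

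Most of this stands, and it rules out three stronger readings.

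- *The plan biases the rate downward.* Downward bias follows from one natural reading of 7.4, not from the text itself. What the documents support is that the rule is unspecified.
- *The open choice is worth 4 to 18 points.* Counting event-free leavers as successes (1 − F: 70.9, 71.8, 73.7%) or as failures (C: 66.5, 63.0, 56.0%) gives spreads of 4.4, 8.8 and 17.7 points. Both assign an outcome to a missing result, which 7.4 appears to exclude, so this spread does not measure what the plan leaves open.
- *Data on leavers are one-sided.* One might argue that safety follow-up after withdrawal can reveal failures, since Section 7.6.2 includes "The proportion of subjects requiring cardioversion through 12 months", while event-free status goes unrecorded. But 5.14 does not say that rhythm monitoring stops, and 5.12.5 has subjects keep the monitor through 12 months. The imbalance is possible but not established.

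The reply does not supply the missing rule. That Kaplan-Meier would be compatible with 7.4 does not mean it is planned; number and percent is what Section 7.3 describes.

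**Conclusion.** The concern holds as a gap in the method. A time-dependent endpoint is to be reported as a proportion in an ITT cohort, with no imputation and no rule for partial follow-up. The direction of bias cannot be fixed from the documents.

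Under the reading that keeps failures and drops event-free leavers, the understatement is about 0.4 to 1.9 points at 70% true freedom and 5–20% yearly random dropout. This rests on assumed dropout, constant hazards and dropout unrelated to outcome. If dropout is related to outcome, any of the methods can be biased either way.

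The consequence is modest: no test or sample size depends on the endpoint, and the effect is well inside sampling error. The change is still worth making because a better estimator is available from data already planned. A reader might extend the point to Chronic Procedural Success, but 7.5.2 defines that endpoint by the remapping procedure, so a denominator of remapped subjects already follows.

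**What to change.** In Sections 7.4 and 7.5.2:

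1. Estimate Therapeutic Success in the ITT cohort by Kaplan-Meier, with 95% CIs at Months 6 and 12.
2. Count AF/AFL/AT or study-device ablation only after the 90-day blanking period. Count a non-study-device ablation during blanking as a failure at the start of the post-blanking period.
3. Use actual event dates. Censor event-free subjects at their last rhythm assessment, defined as a 12-lead ECG, 24-hour monitor or event-monitor transmission.
4. State one rule for applying the ±30-day visit windows, with a separate readout for each landmark. Without it, a subject seen event-free on day 335 would be censored short of day 365 despite attending on schedule.
5. Report how many subjects are event-free with incomplete follow-up. Add a sensitivity bound that counts those without an in-window assessment as failures.
6. Put failures known only from safety follow-up after the censoring date in a sensitivity analysis, not in the main estimate.

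Reporting the number of subjects not remapped alongside Chronic Procedural Success is optional.

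The cost is analysis wording and standard programming. No new data are needed: the weekly event monitoring supplies dates, and Section 11.2.1 already requires the reason for discontinuation. The downsides are slightly more analysis, a less favourable lower-bound figure and reliance on non-informative censoring, which the bound in step 5 helps to probe.
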